Aim 1: Determine the impact of OT on corticolimbic connectivity in alcohol dependent individuals exposed to social stress. Psychophysiological interaction (PPI) analysis using the amygdala as the seed region will be used to assess significant task (stress condition > control condition) x seed interactions. Hypothesis 1A: The OT group will exhibit greater functional connectivity between the amygdala and prefrontal cortical regions (orbitofrontal and anterior cingulate cortices) than the PBO group. Hypothesis 1B: The OT group will report lower subjective anxiety and craving in response to the MIST than the PBO group.

Aim 2: To determine the impact of OT on resting-state functional connectivity in alcohol dependent individuals. Hypothesis 2A: OT will modulate resting-state functional connectivity among sub-networks implicated in reward and motivation (nucleus accumbens, and orbitofrontal cortex), memory and learning (amygdala and hippocampus), and cognitive control (prefrontal cortex and anterior cingulate cortex).

Preliminary Data: Evidence for Corticolimbic Uncoupling During Social Stress in Individuals with SUDs

We examined corticolimbic coupling during the MIST in cocaine-dependent (DSM-4) (n=13) and healthy control (n=15) subjects using a psychophysiological interaction (PPI) analysis. Using the left amygdala as the seed region, significant task x seed interactions were found in both groups (**Figure 1A**). In the cocaine-dependent group, the left amygdala exhibited significantly greater functional connectivity with the posterior cingulate cortex during stress. In the control group, the left amygdala exhibited significantly greater functional connectivity with the orbitofrontal cortex during stress. The MIST produced a significantly greater increase in anxiety in cocaine-dependent individuals than healthy controls (**Figure 1B**). These data provide support and lend feasibility to employing these imaging and stress task procedures in this proposed pilot project.

Approach:

Participants: Twenty-four individuals with AUD will be recruited through the Clinical Intake and Assessment (CIA) Core of the ARC. Screening and basic assessments will be conducted by the CIA Core to determine eligibility and suitability for participation in this pilot project. Each individual will sign an IRB-

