Study Visit Assessments: The Drinking Motives Questionnaire Revised will be used to assess motivation for drinking across four subscales: (1) coping motives; (2) social motives; (3) conformity motives; and (4) enhancement motives [14]. The Form 90 will be used to assess daily alcohol consumption in the 90 days prior to the study visit and the time from last drink [15]. A modification of the Within Session Rating Scale will be used to assess craving and mood [16]. The Childhood Trauma Questionnaire (CTQ) will be used to assess trauma prior to age 18 [24]. To determine MRI safety, the Metal Screening Questionnaire (MSQ) will be filled out by each participant and reviewed by study staff. To assess potential alcohol withdrawal symptoms, the Clinical Institute Withdrawal Assessment of Alcohol Scale, Revised (**CIWA-Ar**) will be administered [30].

Study Visit Procedures: Participants will be asked to arrive at the Addiction Sciences Division on the study visit day. Female participants will have their urine tested for pregnancy. Females who test positive for pregnancy will be excluded. All participants will be tested for drugs of abuse and alcohol. Patients testing positive for drugs, with the exception of marijuana, will be excluded; patients testing positive for alcohol may be re-scheduled. Participants who have not had a physical exam in the Addiction Sciences Division within the last 30 days will have and H&P. Participants will be asked about substance use in the last 90 days and will fill out the Drinking Motives Questionnaire, the CTQ, and the MSQ. They will then be escorted to the scanner at [name].

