The study will use a double-blind placebo controlled design. Intranasal OT (n=12) or PBO (n=12) sprays will be administered at 11:30 am, approximately 45 min prior to the scanning session. This dose and timing of OT administration were selected based on the literature [17, 18]. ***MIST Procedure:*** The study will use a block design of three, 6-min runs separated by 2-min of rest for feedback, for a total of 24 min. During each run, participants will be exposed to 40-sec blocks of three different conditions (rest, control, and experimental). Prior to the task, participants will be shown images of what the screen will look like during each condition. The participants will be instructed to relax during the rest condition and focus on the screen. During the control condition, the participants will be asked to answer math problems as accurately as possible but will also be told that their responses will not be recorded. During the experimental condition, the participants will be asked to perform the math task as quickly and accurately as possible. A performance bar located on the screen will allow them to see their performance as compared to an “average” person. The participants will be told that the average person would answer about 85% of the problems correctly; however, the program limits the participants’ performance rate to between 35-45%. A time limit will be enforced throughout the experimental condition. After each run, the participants will be given negative feedback from the investigator. ***BOLD-fMRI Procedure:*** Data will be acquired on a Siemens Trio 3T scanner in MUSC’s Center for Biomedical Imaging. For co-registration and normalization of functional images, a high resolution T1-weighted MPRAGE anatomical image will be acquired with the following parameters: TR= 2100 ms, TE= 4.18 ms, flip angle= 12°, field of view= 256 mm, slice thickness= 1.0 mm. The scanning planes will be oriented parallel to the anterior commissure–posterior commissure line. Participants will be asked to relax and keep their eyes opened and fixed on a cross-hair for 6 min while resting state data are collected. Participants will then complete the MIST. T2*-weighted gradient-echo planar images (EPI) will be acquired with the following parameters: TR= 2000 ms, TE= 27 ms, flip angle= 76°, matrix 64 x 64, field of view= 23 cm, slice thickness= 3.7 mm with no gap, with 36 slices to cover the entire

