Data Analyses *MIST:* Post-acquisition preprocessing and statistical analysis of all of imaging data will be performed using FEAT (FMRIB Expert Analysis Tool) Version 5.98, part of FSL (FMRIB's Software Library). Data will be preprocessed using scripting tools from FMRIB Expert Analysis Tool (FEAT). Functional connectivity will be measured using a PPI seed-based approach [19]. A customized square wave-form representing the task and the duration of each condition will be convolved with a double-gamma hemodynamic response function. A mask of the seed region will be made using a 12-mm diameter sphere located in the center of the amygdala using the MNI coordinates (x, y, z = ±22, 0, -22). For each participant, the mean corrected and high pass filtered time series of the BOLD signal in the amygdala will be extracted and used in a single subject whole brain PPI analysis. The PPI model will include (1) the task vector; (2) the time series of the BOLD signal in the amygdala; (3) a term representing the positive task x seed interaction; and (4) a term representing the negative task x seed interaction. The first level analysis will generate contrast images of the parameter estimates for each of the four regressors. Since the hypotheses explore increases in corticolimbic connectivity, the group analysis will focus on the positive interaction term. The contrast images of the parameter estimates of the positive interaction term will be entered into a 2nd level random effects analysis. Unpaired t-tests will be used to test for group differences. All group level results will be thresholded at $Z > 2.3$ using a corrected cluster threshold of $p = 0.05$. A linear mixed effects model containing all serially measured time points will be used to assess the effects of OT versus placebo on alcohol craving and anxiety ***Implicit Facial Affect Recognition Task:*** Following preprocessing (described above), within-task data from individual participants will be analyzed with a fixed-effects general linear model (GLM), with each emotion (described below) modeled as a box-car function convolved with a double-gamma hemodynamic response function. The response period at the end of each block will also be modeled as a separate variable to remove effects of explicit decision making and response selection. The GLM procedure is repeated for each voxel with six movement parameters (3 rotation values in radian and 3 translation values in millimeter) included as covariates to control for the influence of head motion on the data. Following first-level analysis, subject-specific contrasts will be entered into second-level, random-effects analyses. Since the hypotheses associated with Specific Aim 2 explore amygdala activity, we will use a region of interest approach (ROI). The BOLD signal from the left amygdala will be extracted using an anatomical mask generated by a 12-mm diameter sphere located in the center of the left amygdala using the MNI coordinates (x, y, z = -22, 0, -22). The percent signal change between the fearful and neutral conditions (contrast of interest) will be calculated for each participant. Separate random-effects one-way analysis of variance tests (ANOVA) will be used to test for the following group differences (AUD-PBO vs. AUD-OT). Since human neuroimaging studies have found that other brain regions play a role in implicit emotional processing, including the right amygdala and insula [27,28], secondary analyses will also include these regions. In addition, OT may impact amygdala responding to happy faces [29] therefore group differences in amygdala responding in the happy-neutral contrast may be explored in future

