2.2 Protections Against Risks

[name] and an on-call physician will be available by pager/cell telephone during the entire study for any questions or emergencies that may arise. Our past research experience suggests that data collection using many of these same assessments and questionnaires can be conducted without undue psychological distress. Efforts will be made to protect the confidential nature of the information collected; however, this

cannot be guaranteed (e.g., subpoena). This experience includes substantial research with individuals with SUDs, healthy controls and work on large-scale studies asking questions about similar topics. At the conclusion of the study visit, each participant will be debriefed and provided with full disclosure about the deception of the MIST. Subjects will be told that the computer makes adjustments to keep the number of correct responses to less than 50% and therefore a good score on the task is impossible. If appropriate, the psychiatrist will personally evaluate the subject. Should any craving or anxiety induced during the experimental manipulation fail to subside within 3-4 hours, a study psychiatrist will be available to arrange either hospitalization through the MUSC CDAP or make an appropriate referral. These protective procedures are in place for all of our on-going research studies of stress reactivity in individuals with SUDs.

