All of the study staff will be required to complete the CBI MRI safety training class. The course is taught by an AART (American Registry of Radiologic Technologists) registered technician. The staff will be trained about safety in the MRI environment, and how to screen oneself and others. The staff will also have knowledge of safety procedures for entering the scanner facility, safely removing participants from the scanner, when and how to quench the magnet and basic emergency procedures including emergency contact information. Standard operating procedures for emergency situations are located on-site. The technician and the PI are authorized to operate the equipment and will be present throughout the scanning sessions. Although there are no known risks of MRI scanning to a developing fetus at 3.0 T, the possibility that risks could be discovered in the future cannot be ignored. Urine pregnancy tests will be used to exclude pregnant women from study participation. A careful metal screening history will be taken from each subject to assess the possibility of metal devices/implants and will be reviewed by the PI, MRI technician and/or clinical staff who have had extensive training and experience with MRI safety. If the screening yields information that raises a question of safety, the subject will be asked to provide the appropriate documentation (i.e. film) before they are allowed to participate. In addition, participants will be asked to empty their pockets and will be screened with a hand-held ferromagnetic-detector wand. Subjects will wear earplugs and sound-dampening headphones to decrease the intensity of the scanner noise. Prior exposure to pictures of the scanner, getting into the scanner and seeing others in the scanner often reduces psychological discomfort or identifies people for whom scanning is not appropriate. If abnormalities in the brain images are found, the subjects will be referred to an appropriate clinical care provider.

Subjects will be informed about the potential symptoms of alcohol withdrawal and advised to call for medical assistance if they experience severe symptoms. The CIWA-Ar will be administered prior to procedures on the study visit day [23].

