5. DATA AND SAFETY MONITORING PLAN (DSMP)

5.1 Summary of the Protocol

The primary objective of this proposal is to identifying the neurobiologic substrates of social stress in individuals with alcohol use disorder. Individuals with alcohol use disorder will receive either intranasal oxytocin (24 IU) or a placebo spray prior to participating in a single fMRI scanning session. During the scanning session participants will complete the Montreal Imaging Stress Task, a Facial Affect Recognition Task, and a resting state scan. The primary outcomes of interest are (1) corticolimbic functional connectivity at rest; (2) corticolimbic functional connectivity during the MIST and (3) subjective anxiety and craving responses to the MIST.

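### Does the mixed model for anxiety and craving need a named contrast and a baseline adjustment before it can test Hypothesis 1B?

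*Combined protocol and SAP*

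**What the plan says.** Hypothesis 1B (under Aim 1) reads: "The OT group will report lower subjective anxiety and craving in response to the MIST than the PBO group". Section 5.1 lists "subjective anxiety and craving responses to the MIST" as the third primary outcome of interest.

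The whole analysis text for this outcome is one sentence at the end of the MIST part of Data Analyses: "A linear mixed effects model containing all serially measured time points will be used to assess the effects of OT versus placebo" on craving and anxiety. It names no fixed effects, tested term, covariance structure or baseline handling.

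On measurement, Study Visit Assessments says "A modification of the Within Session Rating Scale will be used to assess craving and mood", without times. Study Visit Procedures says that before going to the scanner participants "will fill out the Drinking Motives Questionnaire, the CTQ, and the MSQ". The rating scale is not in that list. The list is not exhaustive, though: it also omits the withdrawal scale, about which section 2.2 says "The CIWA-Ar will be administered prior to procedures on the study visit day". The MIST Procedure describes three runs and states "After each run, the participants will be given negative feedback from the investigator", but it places no rating before, between or after the runs.

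The last part of Data Analyses adds a general rule: other baseline characteristics become covariates only if the groups differ significantly on them. Baseline craving and anxiety are not mentioned there.

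**The concern.** The mixed-model sentence can be read in at least four ways: a group main effect over all times, a group-by-time interaction, a difference at one named time, or a model with the arms' baseline means constrained equal. These can give different answers on the same data, and the outcome is listed as primary.

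The wording of Hypothesis 1B, together with the reference in section 2.2 to "craving or anxiety induced during the experimental manipulation", suggests change with the task, so group by time is the natural reading. In a randomised comparison that contrast is valid, but it is usually less precise than adjusting for the baseline rating. With 12 per arm, precision is scarce.

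Timing matters too. A rating taken before the spray allows the total effect of oxytocin to be estimated. A rating taken after the spray but before the task may already carry a drug effect, so an analysis conditioned on it describes reactivity to the task.

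**Working it through.** **Inputs.** From the documents: 12 participants per arm, 24 in total, randomly assigned. The documents give no SD, pre-post correlation, effect size or alpha for this model, and no power figure to reproduce. Assumed here: one pre-spray and one post-task rating, correlation rho between them, k = post SD / pre SD, two-sided 5% tests.

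**Formulas**, in units where the variance of the group difference is the listed quantity times 2/12 (pre SD = 1):

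- change (group by time): k² + 1 − 2·rho·k
- baseline-adjusted: k²(1 − rho²) × f, with f = (24 − 3)/(24 − 4) = 21/20 = 1.05 for estimating the slope

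Without f, change minus adjusted equals (1 − rho·k)², which is never negative. The only possible loss from adjusting is the 5% in f.

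**Equal SDs (k = 1).** The ratio is 1.05(1 + rho)/2.

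| rho | change | adjusted | ratio | 95% half-width, change → adjusted |
|---|---|---|---|---|
| 0.3 | 1.40 | 0.956 | 0.68 | 1.00 → 0.83 SD |
| 0.5 | 1.00 | 0.788 | 0.79 | 0.85 → 0.75 SD |
| 0.7 | 0.60 | 0.536 | 0.89 | 0.66 → 0.62 SD |
| 0.9 | 0.20 | 0.200 | 1.00 | no gain |

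Half-width is t × √(variance × 2/12), with t = 2.074 on 22 df for change and 2.080 on 21 df for adjusted. Break-even is at rho = 2/1.05 − 1 = 0.905.

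**Wider spread after the stressor.**

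| k | rho 0.3 | rho 0.5 | rho 0.7 |
|---|---|---|---|
| 1.25 | 0.82 | 0.94 | 1.03 |
| 1.5 | 0.91 | 1.01 | 1.05 |

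For example, at k = 1.5 and rho = 0.5, change is 2.25 + 1 − 1.5 = 1.75, adjusted is 2.25 × 0.75 × 1.05 = 1.772, and the ratio is 1.01. A stress task may raise spread as well as level, so these rows are as relevant as the equal-SD ones.

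**More than two ratings.** The plan's reference to serial time points suggests several. With one pre rating and the mean of three post ratings, all equally correlated, the ratio is 0.50, 0.66 and 0.81 at rho 0.3, 0.5 and 0.7. The comparator there is a pre-to-mean-post change. A standard group-by-time test over several occasions is a multi-degree-of-freedom test, so these ratios do not describe it.

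**The open choice.** In simulations with no true effect (k = 1, 12 per arm, one pre and one post rating), the main effect, group by time and the post-task difference each reject in about 5% of trials. At least one of the three rejects in 11–12%. Without the main effect, which averages in a pre-treatment rating and so tests Hypothesis 1B poorly, the figure is 8.8–9.4% for rho 0.3 to 0.7.

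**Does the text commit to the less precise option?** No. Keeping every serial rating in the outcome vector is compatible with constraining the arms' baseline means to be equal, and that gives essentially the precision of covariate adjustment. Nothing shows that a baseline rating is left out of the model, or that the significance-based covariate rule applies to it.

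**The case for a change.** The strongest case for a change is that the plan does commit itself elsewhere. The connectivity analysis settles on the positive interaction term, and the faces task names the fearful-versus-neutral contrast. Hypothesis 1B has no counterpart. The choice can also decide the result: with an assumed true post-task difference of 0.8 SD and equal SDs, group by time and the post-only difference disagree on significance in 31%, 34% and 41% of simulated trials at rho 0.3, 0.5 and 0.7. In the same setting, power is 35%, 47% and 68% for group by time against 48%, 56% and 72% with adjustment. Naming a contrast costs only wording, and adjustment risks at most about 5% of variance.

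The omission stands, and so does the arithmetic. It does not show that the plan has chosen badly. The power comparison uses a contrast inferred by the reader and a rating the documents do not place. If no pre-spray rating exists, acting on the point means adding an assessment. If the only earlier rating follows the spray, adjustment answers a different question. The 9–12% figures describe an analyst who tries several tests and reports whichever succeeds. They are not the error rate of any single reading, each of which holds at about 5%. The plan's Bonferroni rule for comparisons outside the a priori hypotheses would not prevent such selection, but nothing in the plan invites it.

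**Conclusion.** No change follows. The rating times and the tested term are indeed unstated, but this is missing detail rather than an error or a stated inferior method. The wording of Hypothesis 1B guides an analyst to a response-to-task comparison, and each single test examined holds its nominal level in this randomised design.

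The precision argument depends on three things the documents do not establish: a pre-spray rating on the same scale, a model that does not already use it efficiently, and a favourable correlation and SD ratio. Under equal SDs with one pre and one post rating, adjustment leaves 68–89% of the change-contrast variance for rho 0.3 to 0.7. With a post SD 1.5 times the pre SD, the gain is about 9% of variance at rho 0.3 and absent at 0.5 and 0.7.

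In a 24-person pilot that states no power, this does not justify revising the plan. When reading the results, check when the ratings were taken: if the reference rating came after the spray, the finding concerns reactivity to the task rather than the total effect of oxytocin.

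### Aim 2 and the first primary outcome are resting-state connectivity, but the only analysis labelled Aim 2 is a face-task amygdala contrast, and no resting-state measure or model is written

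*Combined protocol and SAP*

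**What the plan says.** The Aims section reads "Aim 2: To determine the impact of OT on resting-state functional connectivity in alcohol dependent individuals". It carries a single hypothesis, 2A: "OT will modulate resting-state functional connectivity among sub-networks implicated in reward and motivation". The regions given for that first sub-network are the accumbens and the orbitofrontal cortex. Two further sub-networks, for memory and for control, add the amygdala, hippocampus, prefrontal cortex and anterior cingulate. That is six regions in three sub-networks, with no direction of effect.

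Section 5.1 (Summary of the Protocol) names three primary outcomes: corticolimbic connectivity at rest, the same during the Montreal Imaging Stress Task (MIST), and anxiety and craving responses to the MIST. The face-task response is not among them.

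The BOLD-fMRI Procedure describes the resting scan, with eyes "fixed on a cross-hair for 6 min while resting state data are collected". The design is "Intranasal OT (n=12) or PBO (n=12) sprays will be administered".

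Data Analyses has two headings, MIST and Implicit Facial Affect Recognition Task. Under MIST, "Functional connectivity will be measured using a PPI seed-based approach". Under the face task, "Since the hypotheses associated with Specific Aim 2 explore amygdala activity, we will use a region of interest approach (ROI", followed by an ANOVA of left-amygdala signal change, fearful against neutral.

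**The concern.** The analysis section attaches Aim 2 to a different task, a different kind of measurement (activation, not connectivity) and a different scan from those in the Aims section. The wrong label alone would be a wording correction. The larger problem is that no resting-state analysis appears anywhere else, so the label does not point away from a model that exists.

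Two outcomes are possible. If the plan is followed literally, the trial reports a face-task contrast as its Aim 2 result and leaves Hypothesis 2A and the first primary outcome untested. If a resting analysis is added later, its measure, seed or region masks, first-level model and tested connections are chosen after the protocol, possibly with data in view. Because Hypothesis 2A is non-directional, a difference in either direction on any connection then chosen could be presented as support.

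**Working it through.** The plan gives no figure for this point, so the main check sets its sections side by side.

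**1. What Aim 2 is.** Aims section: resting-state connectivity among six regions. Section 5.1: connectivity at rest is a primary outcome. Face-task paragraph: amygdala activity. The first two agree and the third conflicts with both. No hypothesis in the Aims section concerns amygdala activation; Hypothesis 2A names the amygdala only as one region in a network.

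**2. Whether the PPI can serve at rest.** The PPI has four regressors: task vector, amygdala time series, positive task-by-seed interaction, negative task-by-seed interaction. The resting scan has no task, so the first, third and fourth are undefined (3 of 4). The group analysis focuses on the positive interaction, which is one of these. The amygdala series can be extracted at rest, but no resting model uses it.

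**3. What general text could reach the rest data.**

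| Element | In the plan? |
|---|---|
| Software | Yes: "statistical analysis of all of imaging data will be performed using FEAT" |
| Group-level threshold | Yes: Z > 2.3, corrected cluster p = 0.05, for all group-level results |
| Covariate rule | Yes: baseline variables that differ between arms |
| Multiplicity | Bonferroni, only for comparisons outside the a priori hypothesis |
| Arms and region names | Yes |
| Coordinates | Amygdala only (1 of 6 regions) |
| Connectivity measure | No |
| First-level resting model | No |
| Which connections are tested | No |

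**4. How open the choice of connections is.** Six regions form 6 × 5 / 2 = 15 pairs: 3 within sub-networks and 12 between. The protocol does not define corticolimbic by region. If it means amygdala, hippocampus or accumbens paired with orbitofrontal, prefrontal or cingulate cortex (assumed), there are 3 × 3 = 9 such pairs, of which only accumbens-orbitofrontal lies within a sub-network. Without the accumbens there are 2 × 3 = 6, all between sub-networks.

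**5. Illustration only: error from uncorrected pair tests.** With k independent tests at 0.05, the chance of at least one false positive is 1 − 0.95^k: 14.3% for k = 3 and 53.7% for k = 15. If the statistics correlate at 0.5 (assumed), simulation gives about 12.5% and 36%. Bonferroni over three gives 1 − (1 − 0.0167)^3 = 4.9%.

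**6. Cost of correction.** Two-sided unpaired t-test, 12 per arm, 22 degrees of freedom, noncentrality d × √(12/2). At 0.05, d = 1.197 is detectable with 80% power. At 0.05/3 = 0.0167, it is d = 1.414. Power at d = 1.20 falls from 0.802 to 0.638. These figures apply to single-value tests, not to a cluster-corrected map.

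**The case against.** The strongest defence is that this is a 24-person pilot and that much of the resting analysis is already settled: regions, arms, a 6-minute acquisition, software and a threshold worded to cover all group-level results. That is true, and it rules out the claim that nothing at all is planned for the resting data. It does not answer the point. A software package and a threshold cannot be applied until there is a per-participant quantity to compare, and none is defined. Pilot status does not account for the gap either, since the other two primary outcomes and the unlisted face task all received models.

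Three stronger readings are tempting and should not be drawn.

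- A reader might infer that the first primary outcome carries a false-positive rate of 14% to 54%. The documents do not support this. No section plans separate uncorrected pair tests, and the cluster threshold may apply instead. It is also arguable that pairs Hypothesis 2A does not name fall outside the a priori exemption, so that Bonferroni would apply to them.
- A reader might take Hypothesis 2A to mean the three within-sub-network pairs. The phrase about connectivity among sub-networks suits between-network pairs at least as well, and at most one of the three is corticolimbic. Making those three the primary outcome would set aside the amygdala-frontal connections that Hypothesis 1A names and that carry the study's rationale.
- A reader might infer that the sponsor means to run the PPI on rest data. The PPI stands under the MIST heading and nothing extends it to rest.

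**Conclusion.** The concern holds. The Aim 2 reference in the face-task paragraph contradicts the Aims section and section 5.1, and one of three primary outcomes has no connectivity measure, first-level model or named connections. Followed as written, the only analysis labelled Aim 2 does not test Hypothesis 2A. This goes beyond missing detail and needs correction before unblinding. The conclusion comes from comparing the sections and depends on no numerical assumption. The error rates above show only what could happen if pairs were tested separately without correction. The documents do not settle which connections the sponsor intended, so that choice is the sponsor's to state.

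**What to change.** 1. **Face task.** Remove the Aim 2 attribution and label the task secondary or exploratory.

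2. **Resting-state analysis.** Before unblinding, add one as the test of Aim 2 and the first primary outcome, built from methods already in the plan. Extract the time series from the existing amygdala sphere (side stated), high-pass filter it, and regress out the six movement parameters already used for the face task. Form a whole-brain seed connectivity map for each participant. Compare oxytocin with placebo by unpaired t-test in both directions, at Z > 2.3 with corrected cluster p = 0.05, corrected further for the number of seeds and directions. One seed in two directions gives 0.05/2 = 0.025 per map; left and right seeds tested separately give 0.05/4 = 0.0125.

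3. **Region pairs, if used instead or as well.** An amygdala seed reaches only 5 of the 15 pairs, so the sponsor may want others. Name them in advance, consistent with the corticolimbic wording in section 5.1, and give the mask for each region. Use Fisher-z correlations and apply Bonferroni over the named pairs, stating that this overrides the exemption of a priori comparisons. All other pairs are exploratory. If both the map and the pairs are kept, state which decides the outcome.

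4. **Loose ends.** State whether FEAT or SAS runs tests on extracted values, and that the baseline-covariate rule, if triggered, replaces the t-test with the corresponding linear model.

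The cost is protocol wording, analysis time and the loss of power from correction shown above. No extra scanning is needed, because the resting scan is already scheduled.
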